This is a randomized, controlled, single-center study in otherwise healthy infertile female subjects undergoing in vitro fertilization (IVF). The subjects recruited for this study will be among those patients who have been diagnosed with infertility and are planning to undergo IVF at the center where this study is being performed. The subjects will have undergone the usual informed consent procedure at the center.

Subjects will undergo ovarian stimulation, oocyte retrieval, IVF, and Intracytoplasmic Sperm Injection (ICSI) procedure following the center's usual procedures. At the time of retrieval, participant's oocytes will be randomly assigned to one of two groups: Standard EmbryoScope versus EmbryoScope+. The best quality embryos are selected for embryo transfer and the pregnancy outcome is evaluated.

"Best grade" embryos will be transferred regardless of EmbryoScope use. The standard EmbryoScope as well as the EmbryoScope+ monitor system as assigned during the randomization process will be used to observe the embryo development and document timing of embryo cleavages and morphology dynamics. Subjects will not be provided with the time-lapse images.

Endpoints will be Day 3 and Day 5/6 embryo development, implantation and pregnancy rate. The study is approximately 2 months, the estimated time it takes a physician to perform one IVF-ART treatment cycle. If embryos are frozen, the patient may be in the study until the time they choose to thaw the embryos or up to 1 year if they become pregnant. We aim to compare the current EmbryoScope Time-Lapse System being used in IVF which has become standard of care to the new model EmbryoScope+ to demonstrate that the EmbryoScope+ is as safe and reliable as the EmbryoScope.

Primary Objective:

Comparison of embryo development using standard assessments of morphokinetic parameters, embryo selection algorithms and standard embryo grading.

Secondary Objective:

- 1- Implantation and clinical pregnancy rates
- 2- Embryo transfer rate
- 3- Morphokinetic data
- 4- Frozen embryo transfer outcomes

Statistical Considerations:

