Each subject's oocytes will be randomly divided between the two study arms, resulting in at least 500 oocytes per study arm. With a sample size of 500 oocytes per study arm, a 95% confidence interval for the proportion of oocytes undergoing adequate embryo development (at day 3 and day 5/6) in each study arm can be constructed to be within $\pm 4.4\%$ of the observed proportion of oocytes experiencing adequate embryo development. This calculation assumes an adequate embryo development proportion of 50% to conservatively maximize the width of the obtained confidence intervals. The chi-square test or Fisher's exact test will be used, as appropriate, to compare the adequate embryo development proportion between the Standard EmbryoScope and EmbryoScope+ study arms. Similar analyses will be performed for the secondary endpoints of implantation proportion, pregnancy proportion, embryo transfer proportion, and descriptive morphokinetic data proportions. A univariate generalized estimating equations (GEE) model will also be used to compare the adequate embryo development proportion between the two study arms, correcting for clustering by subject (i.e., multiple oocytes per subject). Lack of any observed statistically significant differences between the two study arms will not constitute evidence of equivalence or non-inferiority between the two study arms; rather, estimates of the adequate embryo development proportion in each group will serve as preliminary data for further investigation (i.e., hypothesis-generating). All p-values will be two-sided with statistical significance evaluated at the 0.05 alpha level. Ninety-five percent confidence intervals for the adequate embryo development proportion, as well as the secondary outcome proportions of interest, will be calculated to assess the precision of the obtained estimates. All analyses will be performed in SAS Version 9.4 (SAS Institute, Inc., Cary, NC) and Stata Version 14.0 (StataCorp, College Station, TX). Note: The statistical considerations section was written in

conjunction with [name], in the Division of Biostatistics and Epidemiology, Department of Healthcare Policy & Research.

Pregnancy Rate will be defined as:

Biochemical pregnancy - positive beta hcg after embryo transfer

Clinical pregnancy - identification of fetal sac in ultra sound post embryo transfer

Ongoing pregnancy - identification of fetal heart in ultra sound post embryo transfer

Delivery rate - live birth

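### The primary objective names embryo grading and selection algorithms, but the primary analyses compare only a yes/no *adequate* proportion, so grade and algorithm score have no planned between-arm comparison

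*Combined protocol and SAP*

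**What the plan says.** All references are to the combined protocol and SAP.

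- **Primary Objective:** "Comparison of embryo development using standard assessments of morphokinetic parameters, embryo selection algorithms and standard embryo grading".
- **Study Design:** the best-graded embryos are the ones chosen for transfer, whichever device they came from ("embryos will be transferred regardless of EmbryoScope use"). Grades are therefore ranked, and the ranking drives selection.
- **Statistical Considerations, first primary analysis:** a chi-square or Fisher's exact test "to compare the adequate embryo development proportion between the Standard EmbryoScope and EmbryoScope+ study arms".
- **Statistical Considerations, second primary analysis:** "A univariate generalized estimating equations (GEE) model will also be used to compare the adequate embryo development proportion between the two study arms", allowing for clustering by subject.
- **Statistical Considerations, secondary endpoints:** similar analyses of "implantation proportion, pregnancy proportion, embryo transfer proportion, and descriptive morphokinetic data proportions".

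Adequacy is assessed at day 3 and at day 5/6, but neither the grades that count as adequate nor the number of grades is given. The same section calls the estimates preliminary and says that a non-significant result is not evidence of equivalence or non-inferiority.

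**The concern.** Two of the three measures named in the primary objective, grading and selection algorithms, do not appear as outcomes in any planned comparison. They may feed into *adequate*, but only after being reduced to yes or no.

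This has two consequences. If one device shifts quality generally, a yes/no outcome uses less of the recorded information than the ordered grade would. If one device moves embryos between grades on the same side of the cut, the primary test cannot register it. With a cut below the top grade, the unseen movement includes a fall from top to middle grade, and the top grade is what feeds transfer. With a cut at the top grade, losses lower down are unseen. Either way, a follow-on study would inherit preliminary data without the grade distribution by arm.

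**Working it through.** **1. The plan's own figure.** Inputs from Statistical Considerations: 500 oocytes per arm ("resulting in at least 500 oocytes per study arm") and an assumed proportion of one half ("This calculation assumes an adequate embryo development proportion of 50% to conservatively maximize the width of the obtained confidence intervals"). Half-width = 1.96 × √(0.5 × 0.5 / 500) = 0.0438, which reproduces the stated ±4.4% "of the observed proportion of oocytes experiencing adequate embryo development". It describes the precision of one arm's yes/no proportion, without clustering, and says nothing about grade or score.

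**2. Objective against analysis.**

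| Named in the Primary Objective | Planned between-arm comparison |
|---|---|
| Morphokinetic parameters | Descriptive proportions, listed with the secondary endpoints |
| Selection algorithms | None, except as absorbed into *adequate* |
| Standard grading | None, except as absorbed into *adequate* |

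**3. Information lost by one cut.** Under proportional odds, the information from ordered categories with shares p is proportional to W = 1 − Σp³. Loss = 1 − W(two classes)/W(all classes). The documents give no shares, so every distribution below is an assumption, listed from the lowest class upwards.

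| Shares (%) | W, all classes | Cut (below/above) | W, two classes | Loss |
|---|---|---|---|---|
| 70/20/10 | 0.648 | 70/30 | 0.630 | 3% |
| 60/20/20 | 0.768 | 60/40 | 0.720 | 6% |
| 50/25/25 | 0.844 | 50/50 | 0.750 | 11% |
| 50/10/20/20 | 0.858 | 50/50 | 0.750 | 13% |
| 50/10/20/20 | 0.858 | 60/40 | 0.720 | 16% |
| 40/15/15/15/15 | 0.9225 | 55/45 | 0.7425 | 20% |
| 40/15/15/15/15 | 0.9225 | 40/60 | 0.720 | 22% |
| Four equal | 0.9375 | 50/50 | 0.750 | 20% |
| Five equal | 0.960 | 40/60 | 0.720 | 25% |

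For a continuous score cut at its median, the loss is 1 − 0.75 = 25% (logistic) or 1 − 2/π = 36% (normal). Off-centre cuts cost more: 40% for four equal grades cut at 25% or 75%, and 50% for five equal grades cut at 20% or 80%.

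**4. What that means for a general shift.** With N = 1000 and V = (N/12) × W, power = Φ(√V × ln OR − 1.96). At an illustrative common odds ratio of 1.43 (ln = 0.3577):

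- yes/no at 50/50: V = 62.5, power 80.7%;
- 50/40/10: V = 67.5, power 83.6%;
- 50/25/25: V = 70.3, power 85.1%;
- four equal grades: V = 78.1, power 88.5%.

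The gain is about 3 to 8 percentage points, ignoring clustering.

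**5. A loss confined to the top grade.** Suppose 40% of top-grade embryos in one arm drop one grade and the cut lies below the top two grades, so the adequate share is unchanged. The yes/no test then rejects at its nominal 5%.

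- *Five levels, 40/15/15/15/15; top grade 15% to 9%.* Top-grade share: pooled SE = √(2 × 0.12 × 0.88/500) = 0.02055 and unpooled SE = 0.02046, so power = Φ((0.06 − 1.96 × 0.02055)/0.02046) = 83%. Ordered comparison: mean rank score moves 0.06 × 0.15 = 0.009, with SE = √(0.9225/12) × √(2/500) = 0.01754. So z = 0.51 and rejection is about 8%.
- *Three levels, 50/25/25; top grade 25% to 15%.* Top-grade share: 98%. Ordered comparison: shift 0.10 × 0.25 = 0.025, SE = √(0.84375/12) × √(2/500) = 0.01677, z = 1.49, rejection about 32%.

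Simulation of the five-level case with clustering (100 subjects, 5 + 5 oocytes, subject SD 0.3 or 0.5, tests on within-subject differences, 3000 trials) agrees: yes/no 5–6%, ordered 8–9%, top-grade share 83–85%.

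**The case against.** **The trial is a pilot.** Sample size rests on interval width, there is no power target, results are labelled hypothesis-generating, and the plan forbids reading non-significance as equivalence. This stands and lowers the stakes. It does not supply the missing grade and score comparison, which is what preliminary data on embryo quality should contain.

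**The loss may be small.** A reader might infer that the yes/no cut always throws away a fifth or more of the information. The documents do not support this: they give no grade distribution, and with a large bottom class of unfertilised or arrested oocytes the loss can be as low as 3%.

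**The cut is undefined.** A reader might also infer that the primary test cannot see any loss of top-grade embryos. That holds only if the cut lies below top grade. If *adequate* meant top grade, the planned test would address exactly that loss.

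**Other comparisons are planned.** It would be wrong to call the adequate proportion the only planned comparison; it is the only one for the primary outcome. The embryo transfer proportion carries indirect information, because sibling embryos compete for transfer on grade. In the five-level scenario with subject SD 0.5, a subject-level test of transfer share rejects about 29% of the time with one embryo transferred and 23% with two (numbers transferred are an assumption). That is more than the ordered model achieves, but far less than the top-grade share. Two assessment days add some staging, but each is still cut once.

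**An ordinal model alone does not cure the main harm.** This is correct in the five-level case (8% against 5%), so the top-grade share has to be an equal part of the remedy.

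**Conclusion.** The mismatch holds on the text alone: the primary objective names selection algorithms and grading, and neither has a planned between-arm comparison beyond whatever enters the yes/no outcome. This is worth correcting but is not a fatal flaw, given the trial's stated exploratory purpose.

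The size depends on assumptions. The information lost is about 3–16% if half or more of the oocytes fall in one bottom class cut at or near its edge, and about 20–36% for roughly equal grades or a continuous score at the best or median cut. The figures assume proportional odds and ignore clustering. Blindness to a fall from top to middle grade does not depend on the grade distribution, but it does require that *adequate* includes more than the top grade.

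**What to change.** In Statistical Considerations, keep the adequate proportion and add the following over all assigned oocytes, with unfertilised or arrested as the lowest category:

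- **(a) Ordered quality.** A cumulative-logit GEE of embryo grade, clustered by subject, and separately a clustered comparison of the algorithm score.
- **(b) Top-grade share.** Each arm's top-grade share per assigned oocyte, with the between-arm difference and 95% CI from the same clustered approach. This stands beside (a) because the ordered model can have little power for a top-grade-only loss.

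Name in advance the grades that count as adequate and as top, separately for day 3 and day 5/6. State that the additions are estimation-focused and hypothesis-generating, in line with the existing text.

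**Cost.** No extra subjects are needed: these are a few more models on assessments the objective already names, extending the clustered GEE already planned. The drawbacks are more estimates to report and a common odds ratio that is less direct to read than a proportion and assumes a similar shift across grades. Reporting the adequate and top-grade shares beside it offsets the latter.

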During in vitro fertilization, human embryos are evaluated to assess their speed and morphological characteristics that allow prediction of their developmental potential and probability to achieve pregnancy and implantation. The advancement of the time-lapse technology enable us to understand the embryo development in vitro. IVF practices is improved by selection of the embryos with the highest implantation potential using time-lapse technology. Automated recording of embryos provides the opportunity to determine the exact timing of embryo cleavages and accurate selection of the viable embryos for transfer. EmbryoScope time-lapse system is the most used for IVF with over 300,000 patient treatments since 2009. The new time-lapse instrument, EmbryoScope+, is the newer model that provides the same result with 3.3 times greater capacity and a more efficient workflow with the automated registration of the EmbryoSlide+ culture dishes. It has been used in Scandinavia in over 500 treatments. We aim to compare the current EmbryoScope Time-Lapse System being used in IVF, which has become standard of care, to the new model EmbryoScope+ to demonstrate that the EmbryoScope+ is as safe and reliable as the EmbryoScope.

Brief study summary including, if applicable:

- Randomization arms: Standard EmbryoScope Time-Lapse system versus EmbryoScope+ on sibling oocytes.
- Length of time on treatment, length of follow-up: 10 months

Brief Summary:

- In-vitro Fertilization (IVF) will be completed according to normal clinical procedures. Participant's oocytes will be randomly assigned to one of two groups: Standard EmbryoScope versus EmbryoScope+.
- The best quality embryos are selected for embryo transfer and the pregnancy outcome is evaluated.
- Study participants will not be compensated.

Key eligibility:**Inclusion:**

40 years of age or younger (maternal)

65 years of age or younger (paternal)
Fresh or frozen (including donor) sperm can be used
Fresh or frozen oocytes (including donor), 10 or more oocytes
ICSI only
Frozen embryos from this study can be included in the outcome portion of this study.

Exclusion:

Patients with less than 10 oocytes
Co-culture patients

Study Design:

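### Cleavage times get no analysis in hours, and the planned clustered model is not extended to the morphokinetic proportions

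*Combined protocol and SAP*

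**What the plan says.** The design compares the devices within subject: "Standard EmbryoScope Time-Lapse system versus EmbryoScope+ on sibling oocytes" (Brief study summary). Under Key eligibility each subject contributes "10 or more oocytes", and under Statistical Considerations each subject's "oocytes will be randomly divided between the two study arms".

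Under Study Design both devices will "document timing of embryo cleavages and morphology dynamics". The Primary Objective is "Comparison of embryo development using standard assessments of morphokinetic parameters, embryo selection algorithms and standard embryo grading". The third Secondary Objective is "Morphokinetic data". The endpoint sentence under Study Design does not name cleavage times: "Endpoints will be Day 3 and Day 5/6 embryo development, implantation and pregnancy rate".

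Statistical Considerations gives chi-square or Fisher's exact test for adequate embryo development and then says: "Similar analyses will be performed for the secondary endpoints of implantation proportion, pregnancy proportion, embryo transfer proportion, and descriptive morphokinetic data proportions". The next sentence adds a GEE model that allows for multiple oocytes per subject, and names adequate embryo development as its only outcome. Further on, 95% intervals are promised for that proportion and for the secondary proportions, as a gauge of precision. No mean, median, time-to-event or hour-scale analysis of cleavage times is given. The plan does not list the morphokinetic items that become proportions.

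**The concern.** There are two gaps.

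1. **No estimate on the time scale.** The trial compares two instruments that record cleavage timing. A comparison of proportions cannot say by how many hours timing differs between them. Proportions suit naturally binary items, and the plan does not say that it will dichotomise times. It simply specifies no analysis of times as times.
2. **Siblings treated as independent.** Oocytes from one subject share biology, and the plan accepts this for its primary proportion. Morphokinetic proportions come from the same siblings, but the tests stated for them assume independence, and the method for their intervals is not stated.

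At stake is the usefulness of the estimates. The plan presents its development results as preliminary data and disclaims equivalence and non-inferiority. In such a study the estimates and their intervals are the main product.

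**Working it through.** **Inputs from the documents:** 100 subjects; about 1000 oocytes; at least 500 per arm; assumed proportion 50%; stated half-width ±4.4%; two-sided alpha 0.05. Hence 1000/(100 × 2) = 5 siblings per subject per arm.

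**Assumed, because the documents give no value:** ICC (ρ) of 0.05 to 0.30, a morphokinetic proportion near 50%, and no subject-by-device variation.

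**1. The plan's own figure.** 1.96 × √(0.25/500) = 4.38 points, so ±4.4% reproduces. It treats oocytes as independent and is stated for adequate embryo development. No precision is stated for any morphokinetic measure.

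**2. Per-arm interval.** With m = 5, the design effect is DE = 1 + (m − 1)ρ = 1 + 4ρ. The half-width is 4.38 × √DE. A simple binomial 95% interval covers 2Φ(1.96/√DE) − 1.

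| ρ | DE | Half-width (points) | Coverage of simple interval |
|---|---|---|---|
| 0.05 | 1.20 | 4.8 | 92.6% |
| 0.10 | 1.40 | 5.2 | 90.2% |
| 0.20 | 1.80 | 5.9 | 85.6% |
| 0.30 | 2.20 | 6.5 | 81.4% |

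More than 10 oocytes per subject are allowed. With 7 per arm (n = 700), the unadjusted half-width is 1.96 × √(0.25/700) = 3.7 points. With DE = 1 + 6ρ it becomes 4.2 points at ρ = 0.05 and 6.2 at ρ = 0.30.

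**3. Device difference, equal split within subject.** The between-arm covariance cancels part of the clustering: Var = 2p(1 − p)/n × [1 + (m − 1)ρ − mρ] = 2p(1 − p)(1 − ρ)/n. The unclustered variance is therefore too large by 1/(1 − ρ). The unclustered half-width is 1.96 × √(2 × 0.25/500) = 6.2 points. The correct one is 6.2 × √(1 − ρ). The actual size of the 0.05 test is 2[1 − Φ(1.96/√(1 − ρ))].

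| ρ | Variance overstated by | Correct half-width (points) | Actual size |
|---|---|---|---|
| 0.05 | 1.05 | 6.0 | 0.044 |
| 0.10 | 1.11 | 5.9 | 0.039 |
| 0.20 | 1.25 | 5.5 | 0.028 |
| 0.30 | 1.43 | 5.2 | 0.019 |

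A beta-binomial simulation (20,000 runs, 100 subjects, 5 oocytes per arm) gave sizes of 0.048, 0.043, 0.030 and 0.018, and per-arm coverage of 92.1%, 89.2%, 84.6% and 80.6%. If each oocyte is allocated independently, the ratio of true to assumed variance is 1.00 at ρ = 0.05 and 0.99 at ρ = 0.30. Neither scheme inflates type I error.

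**4. What a time-scale analysis would deliver.** The half-width for a mean difference is 1.96 × √(2(1 − ρ)/n) in SD units. At ρ = 0.05 and 0.30 this is 0.121 and 0.104 SD with n = 500 per arm. It is 0.171 and 0.147 SD if half reach the stage (n = 250, assumed evenly split). With 500 per arm and ρ = 0.30, an assumed SD of 3 h gives ±0.31 h, 5 h gives ±0.52 h and 10 h gives ±1.04 h.

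**5. If times were dichotomised instead.** For an assumed shift of 0.2 SD (normal times, independence, 500 per arm), power is about 89% on the time scale, 71% with a median split and 62% with a split at the 80th percentile.

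**The case against.** The strongest reply is that this carries little weight. The stated aim is to show that the new model matches the existing one for safety and reliability. The named endpoints are development, implantation and pregnancy. No hour-scale result is promised, and the morphokinetic proportions are labelled descriptive. Timing may already feed into the development outcome through the Primary Objective, and that outcome does get the GEE. The wording about similar analyses is loose enough to allow ordinary summaries of times, or even the GEE. Ignoring siblings does not inflate the device test. The coverage loss requires simple binomial intervals and an ICC that the documents do not give, and at the low end it is small. Per-arm clustering also applies first to the ±4.4% figure. Finally, a timing comparison conditions on reaching the stage, so randomisation does not fully protect it.

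Much of this stands and lowers the severity: the exploratory status, the absence of type I inflation, and the dependence on assumed inputs. It does not close either gap. Even if timing enters the development outcome, a proportion gives no difference in hours. The GEE sentence follows the sentence on secondary endpoints and names one outcome only, so the natural reading excludes morphokinetics. If a wider scope was meant, the text needs to say so.

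**Conclusion.** The concern holds. The plan specifies no analysis of cleavage times on the time scale, and its subject-clustered model does not cover the morphokinetic proportions.

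Under the assumed correlations, simple binomial per-arm intervals would be too narrow: 4.4 points where 4.8 to 6.5 is right. The unclustered device comparison would be valid but, with an equal split, conservative, giving up some of the precision that the sibling design buys (6.2 points against 6.0 to 5.2). The coverage figures apply only if simple binomial intervals are used.

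The plan should be changed, but the gap does not threaten the trial's validity. The endpoint is secondary and descriptive in the analysis text, and no false claim of a device difference follows. The appearance of morphokinetic parameters in the Primary Objective as well is not reconciled with that status, and it makes the missing timing analysis harder to set aside.

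**What to change.** In Statistical Considerations:

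- Keep proportions for naturally binary morphokinetic items, and list those items. Compare the devices, and form the 95% intervals, with the same subject-clustered GEE already planned for adequate embryo development.
- Pre-list a short set of cleavage times. Analyse each with a subject-clustered continuous model: a linear mixed model with device fixed and subject random, or a GEE. Report the mean device difference in hours with 95% CI as a descriptive estimate.
- Beside each timing estimate, report by arm the proportion of all randomised oocytes that reach the stage, and state that the timing comparison is conditional on reaching it.

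The cost is a few lines of text and some extra analysis of data the devices already record; no subjects or procedures are added. The drawbacks are a few more correlated descriptive estimates, and a timing contrast that randomisation does not fully protect.
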